3.7.3. Independent Data Monitoring Committee

During the conduct of this study, an IDMC will review accumulating safety data on a regular basis to ensure the continuing safety of the study patients and review of any study conduct issues.

The IDMC will be composed of independent physicians with expertise in the relevant therapeutic field and other relevant experts, such as a statistician. The IDMC will receive safety data periodically which will be presented by masked treatment groups. They will have the right to recommend modification of the study for safety reasons.

IDMC sessions can be open or closed. During open sessions, representatives of the sponsor may be present, and information is provided and discussed in a blinded fashion. During closed sessions, the only participants are members of the IDMC and the designated unblinded statistician (if approved to be present).

If there is a request to unblind any individual treatment assignment, a written request from the IDMC (as a committee), signed by the IDMC chairperson, should be made to the unblinded statistician. The appropriate medical and operational personnel will be notified but will not receive the unblinded treatment information. Any use of unblinded treatment assignments should be clearly documented and reported to the sponsor at study termination.

The IDMC chairperson will communicate with Nuvelution TS Pharma in regard to issues resulting from the conduct and clinical aspects of the study. Nuvelution TS Pharma and Syneos Health will work closely with the committee to provide the necessary data for review.

The conduct and specific details regarding the IDMC sessions and requests to unblind any blinded treatment assignment are outlined in the IDMC charter.

3.8. Drugs Used in the Study

3.8.1. IMP

The IMP is a matrix formulation and is designed as a gastro-erosional tablet to be administered with food and should not be taken on an empty stomach. The IMP is coated with a white polymer coating to aid in swallowing. TEV-50717 tablets have been manufactured according to current Good Manufacturing Practice regulations. TEV-50717 tablets are available in the following strengths: 6, 9, 12, 15, and 18 mg, all of which are identical in size, shape, and color (white). The IMP will be supplied in 40-count blister packs. The placebo tablets and packaging will match those for TEV-50717. Each blister pack (40-count tablets per dose strength per blister pack) will contain a sufficient supply of drug until the next specified visit/telephone contact, plus overage to account for potential delays in study visits.

A more detailed description of administration procedures is given in Section [5.1](#).

3.8.2. Placebo

Placebo tablets match TEV-50717 tablets. The packaging will be the same as described for TEV-50717 above.

A more detailed description of administration procedures is given in Section [5.1](#).

3.9. Drug Supply and Accountability

3.9.1. Drug Storage and Security

The IMP (TEV-50717 and placebo) should be stored protected from light, at a controlled room temperature, 20°C to 25°C (68°F to 77°F); however, storage between 15°C and 20°C (59°F and 68°F) is acceptable if there is no alternative. The IMP should be stored in a dry, securely locked, substantially constructed cabinet or enclosure with access limited to authorized staff.

3.9.2. Drug Accountability

Each IMP shipment to the site will include a packing slip listing the contents of the shipment, drug return instructions, and any applicable forms.

The investigator is responsible for ensuring that deliveries of IMP and other study materials from the sponsor are correctly received, recorded, handled and stored safely and properly in accordance with the local regulations, and used in accordance with this protocol.

A record of IMP accountability (ie, IMP and other materials received, used, retained, returned, or destroyed) must be prepared and signed by the principal investigator or designee, with an account given for any discrepancies. Empty, partially used, and unused IMP will be disposed of, as agreed with the sponsor/development partner.

3.10. Duration of Patient Participation and Justification

This study will consist of up to a 31-day screening period, a 12-week double-blind treatment period, and a 1-week washout period. Patients who complete the study may be eligible to begin participation in an open-label safety extension study TV50717-CNS-30047 after the end of the washout period. Patients not participating in Study TV50717-CNS-30047 will have a follow-up telephone contact to evaluate safety 1 week after the end of the washout period (2 weeks after their last dose of IMP).

Patients are expected to participate in this study for its entire duration, which is a minimum of 14 weeks. See Section [12.4](#) for the definition of the end of the study.

3.11. Stopping Rules and Discontinuation Criteria

There are no formal rules for early termination of this study. During the conduct of the study, serious adverse events will be reviewed (see Section [7.1.5](#)) as they are reported from the investigational center to identify safety concerns. The study may be terminated by the sponsor at any time.

A patient may discontinue participation in the study at any time for any reason (eg, lack of efficacy, consent withdrawn, and adverse event). The investigator and/or sponsor can withdraw a

patient from the study at any time for any reason (eg, protocol violation or deviation as defined in Section 11.1.2, noncompliance, or adverse event).

Please see Section 4.4 for the withdrawal criteria and procedures.

3.12. Source Data Recorded on the Case Report Form

All patient data must have supportive original source documentation in the medical records, or equivalent, before they are transcribed onto the CRF. Data may not be recorded directly onto the CRF and considered as source data unless the sponsor provides written instructions specifying which data are permitted to be recorded directly onto the CRF, such as eScales.

If patient data are processed from other vendors (eg, clinical laboratory, central ECG, diary data), the results will be sent to the investigational center, where they will be retained but not entered into the CRF. These data may also be sent electronically to the sponsor (or organization performing data management) for direct use with the clinical database (see Section 13.1). All clinical patient data from other vendors will be available to the investigator.

The CRFs are filed in the sponsor's central file after study completion.

3.13. Study Procedures

Study procedures and assessments with their time points are presented in Table 1. During a visit, study procedures and assessments should be performed in the order specified in the study manual.

Detailed by-visit information is provided in the sections following the table. Detailed descriptions of each assessment are provided in Section 6 (efficacy assessments), Section 7 (safety assessments), and Section 8 (pharmacokinetic and other assessments).

Table 1: Study Procedures and Assessments

	Screening	BL ^a	Titration							Maintenance		Follow-up		U
	Up to 31 days	Day 1 ^c	1 (Day 7)	2 (Day 14)	3 (Day 21)	4 (Day 28)	5 (Day 35)	6 (Day 42)	7 (Day 49)	9 (Day 63)	12/ET ^d	13 (Day 91)	14 ^e (Day 98)	
Study week^b														
Visit window (days)		0 days	±3 days										±3 days from Week 12	
In-clinic visit	X ^f	X		X		X		X		X	X	X		X
Telephone contact			X		X		X		X				X	
Evaluate/Adjust IMP			X ^g	X	X ^g	X	X ^g	X	X					X
Informed consent/assent	X													
Eligibility criteria	X	X												
Medical history and psychiatric history	X													
Demographics	X													
Vital signs and weight ^h	X	X ⁱ		X		X ⁱ		X		X	X ⁱ	X		X
Physical examination	X										X			X ^j
Neurological examination	X										X			X ^j
Height	X										X			X ^j
12-lead ECG ^k	X	X				X		X			X			X ^j
Pharmacokinetic blood sampling											X ^l			
Chemistry/Hematology/Urinalysis	X										X	X ^m		X ^j
Urine drug screen	X										X			
Randomization		X												
CYP2D6 genotype ⁿ	X													
β-HCG test ^o	X	X				X					X			X ^j

Table 1: Study Procedures and Assessments (Continued)

	Screening	BL ^a	Titration							Maintenance		Follow-up		U
Study week ^b	Up to 31 days	Day 1 ^c	1 (Day 7)	2 (Day 14)	3 (Day 21)	4 (Day 28)	5 (Day 35)	6 (Day 42)	7 (Day 49)	9 (Day 63)	12/ET ^d	13 (Day 91)	14 ^e (Day 98)	
Visit window (days)		0 days	±3 days										±3 days from Week 12	
MINI Kid ^{p,q}	X													
CDI-2 (Parent and Self-report) ^r	X	X		X		X		X		X	X	X		X ^j
C-SSRS (Children's Baseline/Screen) ^q	X													
C-SSRS (Children's Since Last Visit) ^q		X		X		X		X		X	X	X		X ^j
YGTSS ^{s,t}	X	X		X ^u		X		X ^u		X ^u	X	X ^u		
TS-CGI ^t		X		X		X		X		X	X	X		
TS-PGII ^t		X		X		X		X		X	X	X		
████████ ^t		X		X		X		X		X	X	X		
████████████████		X		X		X		X		X	X	X		
████████████████		X						X ^v			X	X ^v		
C&A-GTS-QOL ^q		X						X			X			
Dispense IMP ^w		X ^x		X ^x		X ^x		X ^y		X ^y				X ^j
Collect IMP				X		X		X		X	X			X ^j
Assess IMP accountability/compliance/supply			X ^z	X	X			X ^j						
Assess adverse events	X	X	X	X	X	X	X	X	X	X	X	X	X	X
Concomitant medications ^{aa}	X	X ^{aa}	X ^{aa}	X ^{aa}	X ^{aa}	X ^{aa}	X ^{aa}	X ^{aa}	X ^{aa}	X ^{aa}	X ^{aa}	X ^{aa}	X ^{aa}	X ^{aa}

^a The baseline visit will occur on the same day as the scheduled first dose of the IMP (day 1).

^b Assessment to occur at the end of the study week.

^c Patients will be provided with a diary to record critical information on dosing. The date and time of the last dose of study medication before the week 12 visit should be recorded in the diary by the patient or caregiver/adult. The site will document the date and time of the sample collection. Prior to the clinic visit on week 12, patients will be reminded to record the start time of their last meal and the time of their last dose in their diary.

^d For patients who withdraw prematurely, an early termination visit should be conducted as soon as possible after the last dose of IMP. All patients who discontinue early will have a follow-up telephone contact for safety evaluation 2 weeks after their last dose of IMP; evaluations will be as described for week 14 (Section 3.13.4.2).

^e This visit is a telephone contact for safety evaluation, required only for patients who will not roll over into the open-label safety extension study TV50717-CNS-30047.

^f The screening visit may be conducted over 2 separate visits at the discretion of the investigator.

^g Dose adjustment will be made by the investigator after telephone contact with the patient and caregiver/adult to evaluate tic reduction and adverse events.

^h Weight must be measured with shoes and outerwear off. Before pulse and BP are measured, the patient must be in a supine or semi-erect/seated position and resting for at least 5 minutes (the same position and arm should be used each time vital signs are measured for a given patient).

ⁱ Orthostatic BP and pulse will be measured after patient is in a standing position for at least 3 minutes.

^j Assessment to be completed at investigator's discretion.

^k All ECGs will be performed after at least 5 minutes rest in a supine or semi-supine position.

^l Two samples will be collected. The first sample will be collected upon arrival at the clinic. The second sample will be collected 2 to 3 hours after the first pharmacokinetic sample collection. Patients with early morning visits (ie, within 2 hours of their scheduled AM dosing) should take their IMP dose in clinic after the first pharmacokinetic sample is collected.

^m Patients with clinically significant laboratory abnormalities at week 12 will have those laboratory evaluations repeated at the week 13 visit.

ⁿ The patient's genotype for CYP2D6 will be blinded during the conduct of the study.

^o For females who are postmenarchal or ≥ 12 years of age, a urine test will be administered at baseline and week 4, while a serum test will be administered at screening and week 12, and if clinically indicated.

^p MINI Kid, (Children and Adolescents) modules to be used are: Major Depressive Episode (Module A), (Hypo) Manic Episode (Module D), OCD (Module J), Alcohol Dependence/Abuse (Module L), Substance Dependence/Abuse (Non-alcohol; Module M), ADHD (Module O), Conduct Disorder (Module P), and Psychotic Disorders and Mood Disorders with Psychotic Features (Module R).

^q For children 13 years of age and under, interviews may be performed separately or jointly with the caregiver/adult as appropriate or defined by the scale. For children over 13 years of age, caregiver/adult involvement is strongly encouraged. Questions should be directed to the child, but the caregiver/adult should be encouraged to add relevant information.

^r Children 6 years of age at baseline will not complete the Self-report version; the caregiver/adult will complete the Parent version.

^s Input from the caregiver/adult is required.

^t The YGTSS, TS-CGI, TS-PGII, and [REDACTED] questionnaires should be performed before any blood draws or ECG assessments.

^u Perform assessment of "Severity Ratings" of the questionnaire. Inventory portions, ie, "Motor Tic Symptom Checklist" and "Phonic Tic Symptom Checklist" do not need to be performed.

^v Perform the Severity Ratings of OCD symptoms (Questions 1 through 10) only. Checklist does not need to be performed.

^w Contact IRT and dispense IMP and patient diary.

^x IMP will be dispensed in the clinic; patients will receive doses for 2 weeks (current dose level and next dose level) to cover the telephone contacts. The site will determine titration (ie, starting the next dose) for the patient by telephone. See Table 2 for baseline weight-based dosing titration.

^y Patients will receive doses for 3 weeks of treatment.

^z The site needs to discuss the drug status during the telephone contacts to ensure the patient has adequate tablets, inform the patient if they should titrate, and remind them to bring used and unused IMP blister packs to the next in-clinic visit.

^{aa} Parents/Patients will be instructed during the course of the study to notify the investigator if any new medication is prescribed, including over-the-counter medications. Any prescribed medication should be reviewed with the investigator.

ADHD=Attention Deficit Hyperactivity Disorder; β -HCG=beta-human chorionic gonadotropin; BL=baseline visit; BP=blood pressure; CDI-2=Children's Depression Inventory, Second Edition, Parent and Self-report Profiles; C-SSRS=Columbia-Suicide Severity Rating Scale; [REDACTED]

[REDACTED] CYP2D6=cytochrome P450 2D6; ECG=electrocardiogram; ET=early termination visit; C&A-GTS-QOL=Child and Adolescent Gilles de la Tourette Syndrome – Quality of Life; IMP=investigational medicinal product; IRT= Interactive Response Technology; MINI Kid=Mini International Neuropsychiatric Interview For Children and Adolescents; OCD=obsessive-compulsive disorder; TS-CGI=Tourette Syndrome-Clinical Global Impression; TS-PGII=Tourette Syndrome-Patient Global Impression of Impact; [REDACTED]; U=unscheduled visit; YGTSS=Yale Global Tic Severity Scale.

3.13.1. Procedures for Screening and Enrollment

A signed and dated informed consent form will be obtained from the parent/legally acceptable representative, and a signed and dated assent, depending on the child's age, as appropriate, will be obtained from each patient before screening procedures commence, according to national laws and local IEC/IRB requirements. Parents/legally acceptable representatives will acknowledge and agree to the possible use of this information for the study by giving informed consent.

A patient who is screened but not enrolled may be rescreened 1 time if there is a change in the status of the patient regarding eligibility for the study. (Note: Details of rescreening must be approved and documented by the medical monitor and/or CST team.)

The screening visit will take place not more than 31 days before the baseline visit. The screening visit may be conducted over 2 separate visits at the discretion of the investigator. The following procedures will be performed at screening:

- obtain written informed consent/assent, depending on the child's age, as appropriate, before any other study-related procedures are performed
- conduct clinic visit
- review eligibility (inclusion and exclusion) criteria
- inform patients of study restrictions and compliance requirements
- review medical and psychiatric history
- review demographics information
- measure vital signs (pulse, BP, body temperature, and respiratory rate)
- perform full physical and neurological examinations (including height and weight. Note: Weight must be measured with shoes and outerwear off)
- perform 12-lead ECG (Note: ECG will be performed after at least 5 minutes rest in a supine or semi-supine position)
- perform clinical laboratory tests, including chemical, hematological, and urine analyses
- obtain a blood sample (3 mL) for analysis of CYP2D6 genotype
- perform urine drug screen (UDS)
- perform a serum pregnancy (beta-human chorionic gonadotropin [β -HCG]) test (only in females who are postmenarchal or ≥ 12 years of age)
- administer the following questionnaires (Note: For MINI Kid and C-SSRS, children 13 years of age and under may be interviewed separately or jointly with the caregiver/adult as appropriate or defined by the scale. For children over 13 years of age, caregiver/adult involvement is strongly encouraged. Questions should be directed to the child, but the caregiver/adult should be encouraged to add relevant

information. The YGTSS questionnaire should be performed before any blood draws or ECG assessments.):

- MINI Kid (Note: The following modules will be used: Major Depressive Episode [Module A], [Hypo] Manic Episode [Module D], OCD [Module J], Alcohol Dependence/Abuse [Module L], Substance Dependence/Abuse [Non-alcohol; Module M], Attention Deficit Hyperactivity Disorder [ADHD; Module O], Conduct Disorder [Module P], and Psychotic Disorders and Mood Disorders with Psychotic Features [Module R])
- CDI-2, Parent and Self-report (Note: Children 6 years of age at baseline will not complete the Self-report version; the caregiver/adult will complete the Parent version.)
- C-SSRS (children's baseline/screening)
- YGTSS (Input from the caregiver/adult is required.)
- review medication history and concomitant medications
- inquire about adverse events

3.13.1.1. YGTSS Rater Certification

All investigators and subinvestigators who will be administering the YGTSS from screening through the end of study visit must undergo and pass a Rater Certification Program which will be provided separately from this protocol. Every effort must be made to ensure that the same certified rater administers the YGTSS to a specific patient at all visits, especially at the baseline and week 12/early termination visits. However, if due to unforeseen circumstances the same rater is absolutely unavailable to complete a visit rating, the YGTSS can be administered only by another certified individual from that study site.

3.13.2. Procedures Before IMP Treatment (Baseline/Day 1)

Patients who meet the inclusion/exclusion criteria at screening will continue to the baseline visit, when baseline evaluations will be conducted.

The following procedures will be performed at baseline:

- conduct clinic visit
- review eligibility (inclusion and exclusion) criteria
- measure vital signs (orthostatic pulse and BP [after standing for at least 3 minutes], body temperature, and respiratory rate)
- measure weight (Note: Weight must be measured with shoes and outerwear off)
- perform 12-lead ECG (Note: ECG will be performed after at least 5 minutes rest in a supine or semi-supine position)
- perform urine pregnancy (β -HCG) test (only in females who are postmenarchal or ≥ 12 years of age)
- randomization with stratification by age at baseline (6 to 11 years, 12 to 16 years)

- administer the following questionnaires (Note: For C-SSRS, [REDACTED] and C&A-GTS-QOL, children 13 years of age and under may be interviewed separately or jointly with the caregiver/adult as appropriate or defined by the scale. For children over 13 years of age, caregiver/adult involvement is strongly encouraged. Questions should be directed to the child, but the caregiver/adult should be encouraged to add relevant information. The YGTSS, TS-CGI, TS-PGII, and [REDACTED] questionnaires should be performed before any blood draws or ECG assessments.):
 - CDI-2, Parent and Self-report (Note: Children 6 years of age at baseline will not complete the Self-report version; the caregiver/adult will complete the Parent version.)
 - C-SSRS (children's SLV)
 - YGTSS (Input from the caregiver/adult is required.)
 - TS-CGI
 - TS-PGII (Input from the caregiver/adult is permitted.)
 - [REDACTED]
 - [REDACTED]
 - [REDACTED]
 - C&A-GTS-QOL
- dispense IMP (patients will receive doses for 2 weeks [current dose level and next dose level] to cover the telephone contacts) and patient diary
- provide patients with a diary to record critical information on dosing
- review concomitant medications
- inquire about adverse events

A patient who is not enrolled in the study on the basis of results of baseline assessments (eg, because inclusion and exclusion criteria were not met or enrollment did not occur within the specified time) may be screened again 1 more time if there is a change in the patient's medical background, a modification of study entry criteria, or other relevant change. (Note: Details of rescreening must be approved.)

Patients will be assigned a permanent unique number at screening (see Section 3.13.1). Patients who continue to meet the inclusion/exclusion criteria at baseline will be randomized to a treatment (active or placebo) using an IRT, and the appropriate IMP will be dispensed.

3.13.3. Procedures During IMP Treatment

3.13.3.1. Titration Period (Baseline/ Day 1 Through 7)

3.13.3.1.1. Telephone Contacts (Weeks 1, 3, 5, and 7)

The following procedures/assessments will be performed via telephone contact at weeks 1, 3, 5, and 7:

- assess IMP accountability/compliance/supply status to ensure the patient has adequate tablets, inform the patient if they should titrate, and remind them to bring used and unused IMP blister packs to the next in-clinic visit
- inquire about adverse events
- review concomitant medications

If a patient experiences an adverse event that is reported during a telephone contact and is probably related to the IMP, he or she will be brought to the clinic for evaluation (see Section 3.13.5). Based on the telephone evaluation, the investigator will determine whether, with the medication already provided, the patient should continue titration or reduce the dose. If additional IMP is required, it would be ordered from the distributor and provided to the patient at an unscheduled visit.

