3.1.3. Titration Period

During the titration period (7 weeks), patients who remain eligible for participation in the study will be randomized in a 1:1 ratio stratified by age (6 to 11 years, 12 to 16 years) at the baseline visit (day 1), and that evening (ie, after the study visit) will receive 6 mg of blinded IMP with food. Tablets should be taken with food (eg, a snack) and should not be taken on an empty stomach. The titration scheme and maximum dose will be determined by body weight and CYP2D6 impairment status at baseline, as shown in [Table 2](#). Patients and their caregiver/adult will interact weekly with the clinical research staff, either by telephone contact or clinic visit from week 1 through week 7 of the titration period, in order to evaluate safety and establish a dose of IMP that optimally reduces tics and is well tolerated (optimal dose). Safety evaluations during titration include assessment of vital signs, monitoring for adverse events and concomitant medications, 12-lead ECGs, and rating scales for depression and suicidality.

In-person (in-clinic) study visits will be scheduled at weeks 2, 4, and 6, and telephone contacts will be scheduled for weeks 1, 3, 5, and 7 in order to assess tic severity and adverse events. The dose of the IMP should be increased on a weekly basis until one of the following criteria is met:

- The investigator determines that there has been a clinically meaningful reduction in tics, as indicated by a sustained reduction in the TS-CGI
- The patient experiences a protocol-defined “clinically significant” adverse event (defined as an adverse event that is related to study medication and is either moderate or severe in intensity or meets the criteria for a serious adverse event).
- The maximum allowable dose is reached, based on the patient’s weight and CYP2D6 impairment status at baseline.

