Although dose adjustments can be made up to and including the week 7 telephone call, if a stable dose is reached before then, the patient should continue on that dose (ie, the dose should not be increased further) for the remainder of the titration period and throughout maintenance dosing, unless there is a change in symptoms during the titration period. If a patient experiences a “clinically significant” adverse event attributable to the IMP, the investigator will determine if a dose reduction or suspension is necessary. If the determination that a patient requires a dose reduction or suspension is made during a telephone contact, an unscheduled clinic visit should be conducted as soon as practicable thereafter.

Dose adjustments should be made based on all available information, including the patient and caregiver/adult reports of adverse events and tic reduction, the clinical assessment of safety and

efficacy by the investigator, and information from rating scales. At the end of the titration period, the patient's dose will be established for the maintenance period.

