3.13.5. Unscheduled Visits

An unscheduled telephone contact may be performed at the discretion of the investigator.

An in-clinic unscheduled visit should be performed if a patient requires a dose adjustment for adverse events reported during a telephone contact. An unscheduled visit may be performed at any time during the study as deemed necessary by the investigator or at the request of the patient or caregiver/adult. The date and reason for the unscheduled visit will be recorded on the CRF as well as any other data obtained (eg, adverse events, concomitant medications and treatments, and results from procedures or tests).

The following procedures/assessments will be performed at in-clinic unscheduled visits:

- conduct clinic visit
- evaluate and/or adjust IMP dose (see Section 5.1)
- measure vital signs (pulse, BP, body temperature, and respiratory rate)

- measure weight (Note: Weight must be measured with shoes and outerwear off)
- inquire about adverse events
- review concomitant medications

The following procedures/assessments may be performed at unscheduled visits per the investigator's discretion:

- measure height
- perform physical examination
- perform neurological examination
- perform 12-lead ECG (Note: ECG will be performed after at least 5 minutes rest in a supine or semi-supine position.)
- perform clinical laboratory tests, including chemical, hematological, and urine analyses
- perform a urine/serum pregnancy (β -HCG) test (only in females who are postmenarchal or ≥ 12 years of age)
- administer the following questionnaires:
 - CDI-2, Parent and Self-report (Note: Children 6 years of age at baseline will not complete the Self-report version; the caregiver/adult will complete the Parent version.)
 - C-SSRS (children's SLV; Note: Children 13 years of age and under may be interviewed separately or jointly with the caregiver/adult as appropriate or defined by the scale. For children over 13 years of age, caregiver/adult involvement is strongly encouraged. Questions should be directed to the child, but the caregiver/adult should be encouraged to add relevant information.)
- dispense additional IMP and patient diary, if applicable
- collect used and unused IMP blister packs
- assess drug accountability/compliance/supply

Other procedures may also be performed at the discretion of the investigator.

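### For a related moderate, severe or serious adverse event reported by telephone, Section 3.13.3.1.1 can be read to let titration continue, although Section 3.1.3 ends escalation at that event

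*Protocol*

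**What the plan says.** **Escalation.** Protocol Section 3.1.3, matched by the synopsis, states: "The dose of the IMP should be increased on a weekly basis until one of the following criteria is met". One of the three criteria is an event that the section calls clinically significant and describes in these words: "defined as an adverse event that is related to study medication and is either moderate or severe in intensity or meets the criteria"; the last limb refers to seriousness. After such an event, "the investigator will determine if a dose reduction or suspension is necessary"; Sections 5.1 and 5.5 say the same.

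**Telephone contacts.** Section 3.13.3.1.1 covers the calls at weeks 1, 3, 5 and 7 and has its own paragraph on adverse events. If the reported event "is probably related to the IMP, he or she will be brought to the clinic for evaluation". On the basis of the call, "the investigator will determine whether, with the medication already provided, the patient should continue titration or reduce the dose". No severity condition is attached. Table 1, footnote x, explains titration by telephone as the start of the next dose.

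**Unscheduled visits.** Section 3.1.3, repeated in 5.5, has: "If the determination that a patient requires a dose reduction or suspension is made during a telephone contact, an unscheduled clinic visit should be conducted". Section 3.13.5 has: "An in-clinic unscheduled visit should be performed if a patient requires a dose adjustment for adverse events reported during a telephone contact". It also lets the investigator arrange a visit at any time.

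**Relatedness.** Section 7.1.4 has two categories, reasonable possibility and no reasonable possibility.

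**The concern.** A site handling a related moderate event on a call finds two instructions. Section 3.1.3 says escalation is over. Section 3.13.3.1.1, the section written for that call, names continuing titration as one of the investigator's choices.

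The issue is practical. At baseline, week 2 and week 4 the family is given both the current and the next dose level, and under Table 2, footnote a, a new dose starts the morning after the call. A decision to continue can therefore take effect before the patient is seen. What is at stake is consistent handling of related events in children during titration, across about 50 planned centers.

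**Working it through.** The plan gives no figure to reproduce here. The check is a comparison of passages plus a reading of Table 2.

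**1. The dose instruction, by type of event**

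| Event reported by telephone | Section 3.1.3 and synopsis | Section 3.13.3.1.1 | Conflict |
|---|---|---|---|
| Related, mild, not serious | Adverse-event criterion not met; increases may go on | Continue titration or reduce | None |
| Related and moderate, severe or serious | Escalation ends; reduction or suspension is the investigator's decision | Continue titration or reduce | Continuing, read as the next dose, is the step that 3.1.3 ends |

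**2. Whether cross-references settle it.** Section 3.13.3.1.1 points to 3.13.5 for the visit, and 3.13.5 points to 5.1 for the dose. Section 5.1 repeats the reduction-or-suspension sentence. It does not restate the criteria that end escalation, and it does not define a clinically significant event. Those appear only in 3.1.3 and the synopsis, so this chain does not reach the stopping criterion.

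**3. Size of the dose difference.** Inputs are the Table 2 maximum daily doses, for a patient on the full schedule. For each call, *hold* is the current row and *continue* is the next row (mg/day).

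| Stratum | Week 1 | Week 3 | Week 5 | Week 7 |
|---|---|---|---|---|
| 20 to <30 kg, not impaired | 6 → 12 | 18 → 18 | 24 → 24 | 30, no later step |
| 20 to <30 kg, impaired | 6 → 12 | 18 → 18 | 18 → 18 | 18, no later step |
| 30 to <40 kg, not impaired | 6 → 12 | 18 → 24 | 30 → 36 | 42, no later step |
| 30 to <40 kg, impaired | 6 → 12 | 18 → 24 | 24 → 24 | 24, no later step |
| ≥40 kg, not impaired | 12 → 18 | 24 → 30 | 36 → 42 | 48, no later step |
| ≥40 kg, impaired | 12 → 18 | 24 → 30 | 36 → 36 | 36, no later step |
| Strata that differ | 6 of 6 | 4 of 6 | 2 of 6 | 0 of 6 |

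Total: 6 + 4 + 2 + 0 = 12 of 24 call-by-stratum cells, each differing by 6 mg/day. Example at week 3, ≥40 kg: hold 24, continue 30, and reduce by the Section 5.1 increment 24 − 6 = 18. Continuing and reducing then differ by 30 − 18 = 12 mg/day. That spread is not general: at week 1, below 40 kg, a 6 mg reduction from 6 mg leaves 0.

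**4. Whether each wording requires an unscheduled visit**

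| Case | 3.13.3.1.1 | 3.1.3 and 5.5 | 3.13.5 |
|---|---|---|---|
| Mild related event, no dose change | Yes | No | No |
| Moderate related event, dose held | Yes | No | Unclear whether a hold is an adjustment |
| Event not rated probably related, dose reduced | No | Yes, as worded | Yes |
| Related event, dose reduced | Yes | Yes | Yes |

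The first trigger depends on the event; the others depend on a dose change. The first also uses *probably related*, which 7.1.4 does not define.

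**The case against.** The best reply is that the sections can be read together. The first bullet of 3.13.3.1.1 has the site tell the patient whether to titrate, so not titrating is an available outcome of the call, and supplying both dose levels makes a hold workable. The disputed sentence is tied to the medication in hand and is followed by one about ordering more. It may be a supply provision rather than a complete list of dose options. On severity it is silent, and silence in a procedures list is weaker than an express contradiction. Section 3.1.3 itself allows a settled dose to change if symptoms change during titration.

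Much of this stands. A reader might infer that holding is impossible at a telephone contact; the bullet shows that it is not. A reader might also infer that the visit rules contradict one another. None says *only*, a site can satisfy all of them by arranging a visit whenever any applies, and 3.13.5 permits discretionary visits.

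What does not fall away is the event-specific sentence. It names continuing titration as a choice, footnote x gives that phrase the meaning of the next dose, and no text says that 3.1.3 controls. A careful investigator may apply 3.1.3, but the protocol does not ensure it.

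**Conclusion.** The point holds in a narrow form. For a related event that is moderate, severe or serious and is reported by telephone, 3.13.3.1.1 can be read to allow an increase that 3.1.3 and the synopsis have ended. It is a wording conflict that can lead to different doses; it does not have to.

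On the full Table 2 schedule the difference between holding and continuing is 6 mg/day in 12 of 24 call-by-stratum cells, at weeks 1, 3 and 5 only. This assumes that the patient is at the table maximum. A patient behind the schedule could face the question at other calls, since adjustments are allowed up to the week 7 call; that is not quantified here. Cells are not patients, and the documents give no expected frequency of such events.

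Two stronger readings are not supported. Four of the seven weekly titration contacts are by telephone, but that does not make the dose conflict a four-call problem on the full schedule. And although the dose at the end of titration is carried into maintenance, nothing in the documents shows an effect on the week 12 result: dosing is flexible and blinded in both arms and is reviewed at each later titration contact. Sample size and power are not involved.

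The differing visit triggers and the undefined relatedness term are secondary points of clarity. The case for change rests on patient safety during titration and the small cost of the correction.

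**What to change.** Reconcile Section 3.13.3.1.1 with Sections 3.1.3, 3.13.5, 5.1 and 5.5 in two respects:

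- Give one statement of what happens to escalation after a clinically significant adverse event, applying equally to events reported by telephone and in clinic, and refer to it from 3.13.3.1.1 and 5.1.
- State the trigger for an unscheduled visit once, using the 7.1.4 relatedness terms in place of *probably related*, and say whether holding the dose counts as an adjustment.

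The sponsor must decide which dose rule and which visit rule stand; this review proposes neither. The cost is a protocol text clarification and a memo to sites, with no new procedures.
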